5.8 Receiving, Storage, Dispensing and Return

5.8.1 Device tracking

Upon receipt of the study treatment supplies, an inventory must be performed and a device receipt log filled out and signed by the person accepting the shipment. It is important that the designated study staff counts and verifies that the shipment contains all the items noted in the shipment inventory. Any damaged or unusable study device in a given shipment (active device or comparator) will be documented in the study files. The investigator must notify study sponsor of any damaged or unusable study treatments that were supplied to the investigator's site.

5.8.2 Storage

The study bone graft material is an approved material of the formulary at the NYU College of Dentistry, and is kept on hand in the clinic dispensary. It is available on demand. Supplies are ordered periodically by authorized staff to ensure availability during the study period.

5.8.3 Dispensing of Study-device

Study bone graft material will be prepared, and implanted into subjects during the sinus augmentation procedure according to randomization protocol. The amount of graft material used usually varies between 4 to 6 grams, depending on the clinical situation, and will be noted in the subject's dental chart and study case report form.

5.8.4 Return or Destruction of Study-Device

At the completion of the study, there will be a final reconciliation of device shipped, device consumed, and device remaining. This reconciliation will be logged on the device log form, signed and dated. Any discrepancies noted will be investigated, resolved, and documented prior to return or destruction of unused study device. Device destroyed on site will be documented in the study files.

Since the study bone graft material is used routinely in the clinic, residual material is discarded. As such there will be no residual study material to reconcile.

CONFIDENTIAL

This material is the property of the NYU College of Dentistry. Do not disclose or use except as authorized in writing by the study sponsor

6 Study Procedures

See an example of such a schedule of events at the end of this document. All procedures are standard of care unless indicated otherwise. All procedures will be performed by the study investigators who are licensed and privileged to do so.

6.1 Screening Visit (Day 0)

Subjects are patients assigned to graduate students within the Program for Advanced Education in Periodontics, an approved program of graduate study within the College of Dentistry. Subjects requiring sinus augmentation and implant placement and who agree to a treatment plan consisting of sinus augmentation and implant placement will be considered for enrollment. Subjects will be screened for eligibility during their clinical care appointment, and if deemed eligible, will be asked by their Graduate student if they are willing to participate in the clinical study. Subjects that meet inclusion and exclusion criteria and sign an approved study informed consent form will be scheduled for sinus augmentation surgery.

Cone beam computed tomography (CBCT) scans are obtained for each patient (NYUCD radiology department). Standardization for the radiographic evaluations and measurements for each patient is made using a radiographic guide. In cases of abnormal thickening of the membrane, suspected cysts or tumors in the sinus, patients are referred to an otolaryngologist (ENT) for consultation and or treatment prior to consideration for sinus augmentation. All patients are prescribed antibiotic and Flonase to be initiated one hour prior to the surgery (Augmentin 875 mg three times a day for 7 days; or ciprofloxacin 500 mg two times a day for 7 days in case of penicillin allergy) in order to minimize risk of infection and to control postoperative discomfort as per standard of care.

- Obtain informed consent of potential participant verified by signature on written informed consent form (Research purposes)
- Obtain demographic information, alcohol and tobacco use history
- Screen potential subjects by inclusion and exclusion criteria (Research purposes)
- Obtain and review medical/dental history, and concomitant medications
- Record blood pressure and pulse
- Standardized peri-apical radiographs, if needed
- Oral examination
- Alginate impressions taken for study model, wax-up, and radiographic/surgical template fabrication if not done prior to the screening visit
- Cone beam computed tomography with radiographic template (if not performed within 12 months prior to screening visit)
- Radiographic/surgical stent fabrication if not done prior to the screening visit
- Provide participants with prescriptions and specific instructions needed to prepare for first study visit

6.2 Visit 1 (Day 1) Randomization - Sinus Augmentation Surgery

All patients are prescribed antibiotic and Flonase to be initiated one hour prior to the surgery (Augmentin 875 mg three times a day for 7 days; or ciprofloxacin 500 mg two times a day for 7 days in case of penicillin allergy) in order to minimize risk of infection and to control postoperative discomfort as per standard care.

The randomization table will be used to assign the two treatment groups to either the right or left side of the mouth.

On the day of the surgical procedure, patients are instructed to rinse with chlorhexidine digluconate 0.12% (Peridex) solution for 30 seconds. Betadine is applied over three quarters of their faces prior to the initiation of the surgery. The procedure is performed under local anesthetic: 2% lidocaine with 1:100,000 epinephrine. A full thickness flap is elevated over the buccal aspect, exposing the lateral wall of the maxillary sinus. An oval-shaped osteotomy is constructed on the lateral surface of the sinus wall using Piezo with sterile saline irrigation. Using specialized curettes, the Schneiderian membrane is carefully elevated and

CONFIDENTIAL

This material is the property of the NYU College of Dentistry. Do not disclose or use except as authorized in writing by the study sponsor

gradually detached along the inferior wall to the medial-anterior walls and extended posteriorly until sufficient space is made for future implant placement. A mixture of 25% small-particle cortical allograft, 25% large-particle cortical allograft, 25% small-particle cancellous allograft, and 25% large-particle cancellous allograft is used for one sinus (Zimmer Biomet). The contralateral sinus will have 100% large particle cancellous allograft (Zimmer Biomet). The allografts are hydrated in sterile saline solution and packed using little pressure from the anterior to the posterior part of the sinus cavity. A resorbable Pericardium membrane (Puros CopiOs pericardium, Zimmer Biomet) is extended at least 3mm beyond the limits of the lateral window. Primary closure of the flap is achieved using 4.0 vicryl sutures. Provisional fixed or removable appliances are relieved over the edentulous areas before reinsertion. Both sinus augmentation can occur on the same visit or can be done on different visits. If the contralateral sinus augmentation surgery is not done at this visit, then the surgery will take place during visit 4.

- Review medical and dental history, and concomitant medications
- Record blood pressure and pulse
- Oral examination
- Local anesthesia administration
- Flap reflection
- Randomization (Research purposes)
- Sinus augmentation surgery (*if possible both sinus augmentation surgery will be performed on the same visit) (Research purposes)
- CBCT immediately after the surgery (Research purposes)
- Oral photographs
- Record adverse events: Subject will be contacted by phone within 24 hours from the surgery: During that conversation, they will be asked if they are experiencing any discomfort, oozing or bleeding, pain, discomfort, numbness of the lip. If anything sounded suspicious, they will be asked to come in for an evaluation.

6.3 Visit 2 (1 week ± 2 days) 1 week Follow-up assessments of study and safety

- Review medical and dental history, and concomitant medications
- Record adverse events as reported by participant or observed by investigator (Research purposes)
- Oral examination and evaluation of the surgical area
- Assessment of the healing process
- Documentation of any possible complications
- Standardized peri-apical radiographs, if needed
- Oral photographs

All patients are provided with verbal and written post-operative instructions following the sinus augmentation procedure. Patients are instructed to continue the antibiotic regime for a total of 14 days and to take Ibuprofen 800 mg as needed for pain management. Patients are seen for evaluation one week after the surgery. Sinus augmentation on the contralateral side is done no later than 6 weeks following the first surgery.

6.4 Visit 3 (2 week ± 2 days) 2 week follow-up assessments of study and safety

Sutures are removed at a two-week follow-up visit.

- Review medical and dental history, and concomitant medications
- Oral examination
- Record adverse events as reported by participant or observed by investigator (Research purposes)
- Removal of sutures
- Standardized peri-apical radiograph, if needed
- Oral photographs

CONFIDENTIAL

This material is the property of the NYU College of Dentistry. Do not disclose or use except as authorized in writing by the study sponsor

6.5 Visit 4 (4 weeks \pm 7 days) Possible Sinus Augmentation of contralateral sinus (*This visit is only done if the Sinus Augmentation of contralateral sinus was NOT performed during visit 1)

At this visit, the second sinus augmentation is performed if the contralateral sinus augmentation were not performed together during visit 1. The initial randomization scheme determines which treatment will be done on this site. The surgical preparation is done as above for the initial sinus augmentation surgery.

- Review medical and dental history, and concomitant medications
- Record of blood pressure and pulse
- Oral examination
- Local anesthesia administration
- Flap reflection
- Contralateral sinus augmentation surgery - (Research purposes)
- Standardized peri-apical radiographs, if needed
- CBCT immediately after the surgery (Research purposes)
- Oral photographs
- Record adverse events (Research purposes)
- Subject will be contacted by phone and 24 hours from the surgery: During that conversation, they will be asked if they are experiencing any discomfort, oozing or bleeding, pain, discomfort, numbness of the lip. If anything sounded suspicious, they will be asked to come in for an evaluation.

(*perform only if contralateral sinus augmentation is performed during this visit)

6.6 Visit 4A (5 weeks \pm 2 days) 1 week after contralateral surgery Follow-up assessments of study and safety – (*This visit is only done if the Sinus Augmentation of contralateral sinus was performed during visit 4)

- Review medical and dental history, and concomitant medications
- Record adverse events as reported by participant or observed by investigator (Research purposes)
- Oral examination and evaluation of the surgical area
- Assessment of the healing process
- Documentation of any possible complications
- Standardized peri-apical radiographs, if needed
- Oral photographs

6.7 Visit 4B (6 weeks \pm 2 days) 2 weeks after contralateral surgery Follow-up assessments of study and safety – (*This visit is only done if the Sinus Augmentation of contralateral sinus was performed during visit 4)

Follow up care and suture removal is performed following the sinus augmentation

- Review medical and dental history, and concomitant medications
- Record blood pressure and pulse
- Record adverse events as reported by participant or observed by investigator (Research purposes)
- Oral examination and evaluation of the surgical area
- Assessment of the healing process
- Documentation of any possible complications
- Standardized peri-apical radiographs, if needed
- Suture removal
- Oral photographs

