5.7 Randomization

This is a single (subject) masked study. Subjects will be unaware of which side of their jaw received which type of bone grafts. Laboratory technicians will be masked when analyzing the bone core samples.

Each tooth sites will be randomized 1:1 into one of the following bone grafts:

- Bone graft A: A mixture of 25% small-particle cortical allograft, 25% large-particle cortical allograft, 25% small-particle cancellous allograft, and 25% large-particle cancellous allograft is used for one sinus (N=10).
- Bone graft B: 100% large particle cancellous allograft for the contralateral sinus (N=10).

A randomization schedule established by an independent statistician affiliated with the New York University College of Dentistry.

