8.4 Unblinding Procedures

In the event of an SAE the PI will be unblinded with regard to the randomization assignment. The unblinding will be reported to the IRB within 24 hours. A written narrative of the event will be submitted to the sponsor within 48 hours of the unblinding.

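### Visit 1 lists randomization before membrane elevation and nothing masks the surgeon, so drawing one step later would be a cheap, optional safeguard

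*Combined protocol and SAP*

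**What the plan says.** **Order of steps.** The bulleted list for Visit 1 (section 6.2) runs: flap reflection, then "Randomization (Research purposes", then the sinus augmentation surgery. The narrative in the same section mentions the allocation before it describes any surgical step: "The randomization table will be used to assign the two treatment groups to either the right or left side of the mouth". It then describes the flap, the window osteotomy and the elevation, and only afterwards the grafting. On elevation it says "Using specialized curettes, the Schneiderian membrane is carefully elevated", and that this continues "until sufficient space is made for future implant placement". Section 1.5 also treats elevation as part of the sinus augmentation procedure.

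**Masking.** Section 5.7 states "This is a single (subject) masked study" and adds "Laboratory technicians will be masked when analyzing the bone core samples". Section 4.3 says the bone specimens are coded so that neither laboratory staff nor clinical investigators can identify them. Section 8.4 says "In the event of an SAE the PI will be unblinded with regard to the randomization assignment". The opening of section 6 says "All procedures will be performed by the study investigators who are licensed and privileged to do so".

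**Perforation.** Section 1.5 puts the risk of membrane perforation at 20%. Depending on its extent, a perforation may mean stopping and re-elevating four months later. The share of perforations that lead to an abort is not given.

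**Staged second side.** Under section 6.5, a contralateral sinus operated at Visit 4 receives the graft already fixed by the initial randomization.

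**The concern.** Two discretionary decisions come after the listed draw and before any graft is placed: how far to elevate, and whether a perforation aborts the sinus. Neither requires knowledge of the arm. In a split-mouth trial the contrast relies on the two sides being prepared alike, and the investigators have a stated expectation: section 1.1 reports early results suggesting that adding small particles yields more new bone without volume loss.

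The more direct path is to the secondary outcome. Elevation creates the space the graft fills. The CBCT taken immediately after surgery records the height reached (section 1.5), and that scan is the starting point for the later height and volume comparison (sections 3.3 and 7.2).

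A path to histology is conditional. An aborted sinus is re-elevated four months later, while Visit 6 collects cores from both sinuses at 8 months. If Visit 6 is not rescheduled, which the protocol does not address, that side would have about 8 − 4 = 4 months of healing. Masked reading of the cores could not remove such a difference.

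**Working it through.** The plan gives no figure for this point, so the check is a reading of the text plus a count of the decisions involved.

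**1. Is the draw listed before elevation?** Yes. The 6.2 list has the draw between flap reflection and surgery, and 6.2 and 1.5 place elevation inside the surgery. The 6.2 narrative does not contradict this.

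**2. Is the surgeon masked?** Not stated.
- 5.7 covers subjects and laboratory technicians.
- 4.3 covers the coded cores, not the allocation at surgery.
- 8.4 implies a principal investigator who is blinded until a serious adverse event. It does not identify that person as the surgeon and does not describe withholding the assignment during the operation. It also sits awkwardly with the subject-only label in 5.7.
- Section 6 says only that study investigators operate.

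No section says who reads the randomization table or when the surgeon is told. The text therefore supports that the surgeon may know, and no more.

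**3. How many elevations are affected?** Inputs: 10 subjects, two sinuses each.
- Elevations after the draw, in list order: 10 × 2 = 20.
- Elevations before the draw if it is moved: at least 10 (the first-operated sinus in each subject). The maximum is 20, if every subject has same-day surgery and both sinuses are elevated first.

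**4. How many perforation judgments might arise?** Input: 20% (section 1.5). The text does not say whether this is per sinus or per patient, so both readings are shown.

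| Reading of 20% | Risk per sinus | All 20 sinuses | 10 first-operated sinuses |
|---|---|---|---|
| Per sinus | 0.20 | 20 × 0.20 = 4.0 | 10 × 0.20 = 2.0 |
| Per patient, sides equal and independent | q = 1 − √(1 − 0.20) = 0.1056 | 20 × 0.1056 = 2.11 | 10 × 0.1056 = 1.06 |

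Check on the second row: 10 × (1 − (1 − 0.1056)²) = 2.0 subjects with a perforation, which is 20% of 10.

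Share guaranteed to fall before the draw: 2.0/4.0 = 1.06/2.11 = 50% under either reading.

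These are expected perforations, not aborts. They are an upper limit on the abort decisions open to influence and say nothing about the size of any effect.

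**The case against.** The opposing case is substantial.

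- **No problem is demonstrated.** The stated criteria for both decisions (enough space for the implant; extent of the perforation) are the same for either graft. This stands, and it is why the point is optional.
- **Primary outcomes are largely protected.** Core readers are masked, specimens are coded, every subject receives both grafts, an aborted side is delayed and not dropped, and section 7.3 analyses all randomized subjects. This stands, apart from the conditional healing-time issue.
- **Each sinus is its own CBCT baseline.** A difference in initial space does not by itself create a difference in change over time. This stands and weakens the secondary-outcome path.
- **Stronger arm-aware steps remain.** The surgeon sees the graft when packing it, the amount varies from 4 to 6 g with the clinical situation (5.8.3), and no masking is stated for CBCT measurement. A later draw touches none of these. This stands.
- **The list may not be a timing script, and the draw is already intraoperative.** This is fair. The schedule comes from an independent statistician, and in list order the flap is reflected before assignment. But the text does not say that the assignment is withheld any longer than that.

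A reader might infer that the surgeon is in fact unmasked during elevation. The documents do not say so; they are silent on when the surgeon is told, and 8.4 points the other way for the principal investigator. A reader might also infer that a later draw closes the route. It does not, because the second sinus is unprotected in staged subjects and in same-day subjects operated in sequence, as is an aborted sinus re-entered after its partner has been grafted.

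**Conclusion.** The point holds as a low-severity, optional improvement. As written, the draw precedes membrane elevation, and nothing prevents the surgeon from knowing the assignment during two decisions that do not need it. Moving the draw guarantees protection for the first-operated sinus only: at least 10 of 20 elevations, and about half of the expected 4.0 (or 2.1) perforation judgments.

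A reader might conclude that the trial's results are biased. The documents do not support that: they do not show that either decision would differ by arm, and they give no figure from which a bias could be computed.

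The conclusion assumes that the Visit 1 list reflects the intended sequence and, for the perforation counts, one of the two readings of the 20%. If the surgeon is in practice told only after elevation, the remaining task is to write that down.

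**What to change.** - **Section 6.2:** move the randomization item to after membrane elevation and the perforation check of the first-operated sinus, before any graft is opened or mixed.
- **Section 5.7:** state that the surgeon learns the assignment only at that moment, and who provides it.
- **Aborted first sinus:** keep the allocation closed until a sinus is elevated and ready to graft. The aborted side later receives the graft that the schedule gives that side.
- **Same-day surgery:** elevating both sinuses before the draw is optional, at the surgeon's discretion.

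The cost is a short wait with the elevated sinus open while the allocation is read and the graft is mixed and hydrated; the protocol does not say how long that takes. Someone must be present to give the assignment. There is a small saving if the first sinus is aborted: the package insert (Attachment B) does not allow opened graft to be kept for another procedure, so opening it later avoids waste. Sample size and analysis are unchanged. Packing and graft amount remain unmasked.

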6.8 Visit 5 (7 month \pm 2 weeks) Pre-implant placement Visit and CBCT

Prior to the implant placement, a post-operative CBCT is taken as part of standard of care in order to determine the clinical outcome of the sinus augmentation bone graft and the clinical situation.

CONFIDENTIAL

This material is the property of the NYU College of Dentistry. Do not disclose or use except as authorized in writing by the study sponsor

- Review medical and dental history, and concomitant medications
- Record blood pressure and pulse
- Record adverse events as reported by participant or observed by investigator (Research purposes)
- Oral examination and evaluation of the surgical area
- Assessment of the healing process
- Documentation of any possible complications
- Standardized peri-apical radiographs, if needed
- Oral photographs
- CBCT
- CBCT review to determine the clinical outcome and the type of implant to be ordered
- Order of implants
- Provide participants with prescriptions and specific instructions needed to prepare for implant surgery

6.9 Visit 6 (8 month \pm 7 days) Implant placement and bone core collection from both sinuses

Patients are instructed to rinse with chlorhexidine digluconate 0.12% (Peridex) solution for 30 seconds. Betadine is applied over three quarters of their faces prior to the initiation of the surgery. The procedure is performed under local anesthesia: 2% lidocaine with 1:100,000 epinephrine. In case of severe anxiety, implants can be placed while patients are under conscious sedation. A crestal incision is made and a full-thickness envelope flap is elevated. A surgical guide is used for both core harvesting and implant placement. Using a trephine bur similar in width to the 2.5mm pilot drill, a bone core of at least 5mm long is harvested from inside the grafted sinus (Research purposes). Following core harvesting, the bone cavity is further prepared for a dental implant (Zimmer Biomet Trabecular Metal Dental Implant) and the implant is placed according to the manufacturer's recommendations.

The harvested bone core is fixed in 10% buffered formalin for 10 to 12 hours and cut into thinly ground longitudinal sections using a precision cutting instrument (Microtome; NanjingEverich Medicare Import & Export, Co., Ltd, Nanjing, China). The specimen is dehydrated in an ascending series of alcohol rinses and embedded in a glycolmethacrylate resin (Techonovit 7200 VLC; Kulzer, Wehrheim, Germany). After polymerization, the specimen is longitudinally cut into 150-mm-thick sections with a high-precision diamond disc and then ground down to about 30 mm in thickness with a specially designed grinding machine. The resulting slides are stained with hematoxylin and eosin and sent to the pathology department at NYUCD for histologic analysis. Quantitative histomorphometry is conducted using software (OsteoMeasure; OsteoMetrics, Inc., Atlanta, GA), which interfaces with a light fluorescence microscope (eg, Olympus TIRFM; Olympus Corporation, Tokyo, Japan) and digital camera (e.g., Olympus Microfire; Olympus Corporation). Quantitative histology of hematoxylin and eosin-stained slide sections is assessed according to the methods of Parfitt et al. for various histology features and scored using a stratified 5-point scale and a simplified 2-point scale that collapsed findings into 2 broad categories for clinical relevance.

Primary closure of the flap is achieved using 4.0 vicryl sutures. Provisional fixed or removable appliances are relieved over the edentulous areas before reinsertion.

All subjects are provided with verbal and written post-operative instructions following the implant procedure. Subjects are instructed to continue the antibiotic regime for a total of 14 days and to take Ibuprofen 800 mg as needed for pain management.

- Review medical and dental history, and concomitant medications
- Record blood pressure and pulse
- Oral examination
- Local anesthesia administration
- Flap reflection
- Bone core collection with trephine bur (Research purposes)
- Implant placement (Zimmer Biomet Trabecular Metal Dental Implant)

CONFIDENTIAL

This material is the property of the NYU College of Dentistry. Do not disclose or use except as authorized in writing by the study sponsor

- Standardized peri-apical radiographs, if needed
- Oral photographs
- Record adverse events: Subject will be contacted by phone and 24 hours from the surgery: During that conversation, they will be asked if they are experiencing any discomfort, oozing or bleeding, pain, discomfort, numbness of the lip. If anything sounded suspicious, they will be asked to come in for an evaluation.

6.10 Visit 7 (8 month + 2 weeks \pm 2 days) 2 weeks after surgery follow-up and suture removal

Sutures are removed at two-week follow-up visit. Oral hygiene instructions are given.

- Review medical and dental history, and concomitant medications
- Record blood pressure and pulse
- Record adverse events as reported by participant or observed by investigator (Research purposes)
- Oral examination and evaluation of the surgical area
- Standardized peri-apical radiographs, if needed
- Assessment of the healing process
- Documentation of any possible complications
- Oral photographs
- Suture removal

